4.3. Justification for Dose

Doses and dosing scheme presented are projected based on nonclinical data and may be modified based on emerging safety, tolerability, and PK data.

4.3.1. Prediction of Human Pharmacokinetics

PF-07059013 binds ditopically and cooperatively to Hb (2 drug molecules/Hb tetramer) as evidenced by a concentration dependent decrease in blood fraction unbound in vitro and in vivo. A 2-step binding Hb model was developed and applied to PF-07059013 blood binding data in multiple species which accounted for this concentration dependency.

Human PK was predicted using a minimal physiologically-based pharmacokinetic (PBPK) model that utilizes in vitro data and SimCYP predictions, and incorporates the binding to Hb. As a result of concentration dependent Hb binding properties of PF-07059013, non-linear concentration dependent PK profile is projected. Dose-dependent decrease in apparent blood clearance (CL) and V_{ss} is projected. Effective half-life predicted from the model ranges from 7 hours at 100 mg to 41 hours at 3000 mg for healthy participants.

4.3.2. Prediction of Efficacious Dose/Concentration

Efficacious concentration is defined as average concentration at the dose resulting in approximately 25% Hb coverage in sickle cell patients at steady state – a coverage level expected to significantly reduce RBC sickling and improve Hb levels in SCD patients.^{14,15} Using the minimal PBPK model and ditopic Hb binding affinities for PF-07059013, the steady state average concentration meeting this objective is predicted to be 0.16 $\mu\text{g}/\text{mL}$ unbound plasma and 260 $\mu\text{g}/\text{mL}$ blood total drug achieved at 1500 mg QD oral dose. The associated unbound plasma C_{max} and unbound plasma AUC_{24} are projected to be 0.18 $\mu\text{g}/\text{mL}$ and 3.9 $\mu\text{g}\cdot\text{hr}/\text{mL}$ respectively.

4.3.3. Dose Selection

Projections of human PK exposure for PF-07059013, along with the toxicity study data, and a minimal anticipated biological effect level (MABEL) approach, based on projected Hb coverage, are used to establish the nominal dose range to be studied in Part 1 (single escalating doses) and Part 2 (repeated escalating doses), with the aim to bracket the expected clinically efficacious dose range in humans and provide safety coverage for a wide range of predicted levels of Hb coverage. Approximately 40% Hb coverage has been previously

studied in healthy adult participants, for compounds with the same pharmacological mechanism, with no safety concerns detected.^{16,17}

4.3.3.1. Rationale for Dose Selection in Part 1

Based on PK and Hb coverage predictions from the minimal PBPK model, 100 mg is proposed as the starting dose in Part 1. A single oral dose of 100 mg is predicted to provide maximum Hb coverage of less than 0.5%, and >66-fold safety margin relative the PK stopping limits (refer to Table 1). To account for uncertainty in the prediction of unbound intrinsic clearance using human hepatocytes, sensitivity analysis was performed assuming 30% lower unbound intrinsic clearance. Projected maximum Hb coverage based on this assumption is less than 0.7%. Considering the precedence of the pharmacological mechanism, along with the projected safety margins and Hb coverage, the starting dose of 100 mg is anticipated to be safe and have minimal pharmacological effect.

The planned dose escalation procedure will be dictated by the rules summarized in [Section 6.6.1](#) and is aimed to occur in increments of $\leq \frac{1}{2}\text{-log}$ (ie, 3.3-fold) based on predicted unbound exposure, with smaller increments envisioned at higher doses, and will not exceed unbound exposures defined in the PK stopping limits (See [Section 6.6.1](#)), or the highest practical dose of 4000 mg, whichever is the most conservative.

At the current proposed maximum single dose of 3000 mg, projected Hb coverage is 23%, and >5-fold safety margin relative to the PK stopping limits is predicted. Projected exposure of PF-07059013 at each planned dose level, as well as corresponding safety margins relative to exposures at the NOAEL in dog are summarized in Table 1. The PK stopping limits were chosen based on unbound PF-07059013 exposure achieved at the NOAEL dose (1000 mg/kg/day) in the 30-day toxicity study in dog, which provides more conservative margins than mouse NOAEL dose— refer to [Section 2.2.3](#).

Table 1. Predicted Human Exposure and Safety Margins Following Administration of Single Oral Doses of PF-07059013, in Part 1

Dose ^a (mg)	Predicted Human Exposure of blood and plasma PF-07059013 ^b						Predicted Safety Margin based on unbound PF-07059013 ^c		Max Hb coverage (%)
	Blood C _{max} ($\mu\text{g}/\text{mL}$)	Plasma C _{max} ($\mu\text{g}/\text{mL}$)	Unbound C _{max} ^d ($\mu\text{g}/\text{mL}$)	Blood AUC ₂₄ ($\mu\text{g}\cdot\text{hr}/\text{mL}$)	Plasma AUC ₂₄ ($\mu\text{g}\cdot\text{hr}/\text{mL}$)	Unbound AUC ₂₄ ^d ($\mu\text{g}\cdot\text{hr}/\text{mL}$)	C _{max}	AUC ₂₄	
100	6.8	0.14	0.0227	81	2	0.324	66.1	69.4	0.47
250	21	0.26	0.0421	310	4.4	0.713	35.6	31.6	1.4
500	48	0.39	0.0632	820	7.5	1.22	23.7	18.5	3.2
1000	110	0.59	0.0956	2000	12	1.94	15.7	11.6	6.9
2000	230	0.91	0.147	4600	19	3.08	10.2	7.31	15
3000	370	1.2	0.194	7300	26	4.21	7.72	5.34	23

Table 1. Predicted Human Exposure and Safety Margins Following Administration of Single Oral Doses of PF-07059013, in Part 1

Dose ^a (mg)	Predicted Human Exposure of blood and plasma PF-07059013 ^b						Predicted Safety Margin based on unbound PF-07059013 ^c	Max Hb coverage (%)
	Blood C _{max} (μ g/mL)	Plasma C _{max} (μ g/mL)	Unbound C _{max} ^d (μ g/mL)	Blood AUC ₂₄ (μ g·hr/mL)	Plasma AUC ₂₄ (μ g·hr/mL)	Unbound AUC ₂₄ ^d (μ g·hr/mL)		

- a. Depending on the available safety and PK data, dose escalation may be adjusted to doses other than those outlined above with intermediate doses evaluated instead of or in addition to the planned dose levels with increments being $\leq 1/2$ -log (ie, 3.3-fold) while following dose escalation and stopping rules outlined in [Section 6.6.1](#).
- b. Human exposure was predicted based on a minimal PBPK model using in vitro data and SimCYP predictions.
- c. Derived using exposure of PF-07059013 at NOAEL (1000 mg/kg/day) from 1 month dog toxicity study of unbound C_{max} = 1.5 μ g/mL and AUC₂₄ = 22.5 μ g·hr/mL.
- d. Unbound values calculated taking into account plasma protein binding in humans(f_{up}=0.162).

4.3.3.2. Rationale for Dose Selection in Part 2

Initiation of dosing in Part 2 will occur following review of safety and PK data from both cohorts in Part 1 Period 4 (see [Section 4.1](#)). At the starting dose level for Part 2, projected unbound exposures (C_{max} and AUC) at steady-state will be covered (approximately 2-fold lower) by exposures observed to have an acceptable safety profile in Part 1 of this study. Projected Hb coverage will not exceed that from Part 1, and will not be higher than 15%.

The proposed starting dose in Part 2 is 600 mg QD. At this planned initial dose level, projected maximum Hb coverage is 7.4%, and predicted steady-state unbound exposures are C_{max} of 0.0972 $\mu\text{g}/\text{mL}$ and AUC_{24} of 1.94 $\mu\text{g}\cdot\text{h}/\text{mL}$ (>11-fold exposure multiples relative to the PK stopping limits). Planned dose escalation procedure will be dictated by the rules summarized in [Section 6.6.1](#) and is aimed to occur in increments of $\leq\frac{1}{2}\text{-log}$ (ie, 3.3-fold) based on predicted unbound exposures, with smaller increments envisioned once the projected clinically efficacious dose is exceeded, and will not exceed the predefined PK stopping limits ([Section 6.6.1](#)), or the highest practical dose of 4000 mg, whichever is the most conservative. The proposed nominal doses, corresponding projected PK exposures based on QD dosing, and safety margins relative to PK stopping limits set based on NOAEL from dog are summarized in Table 2.

Table 2. Predicted Human Exposure and Safety Margins Following Administration of Multiple Oral QD Doses of PF-07059013 for 14 Days, in Part 2

Dose ^a (mg)	Predicted Steady-State Human Exposure of Blood and Plasma PF-07059013 ^b						Predicted Safety Margin at Steady State based on unbound PF-07059013 ^c		Max Hb coverage (%)
	Blood C_{max} ($\mu\text{g}/\text{mL}$)	Plasma C_{max} ($\mu\text{g}/\text{mL}$)	Unbound C_{max}^d ($\mu\text{g}/\text{mL}$)	Blood AUC_{24} ($\mu\text{g}\cdot\text{hr}/\text{mL}$)	Plasma AUC_{24} ($\mu\text{g}\cdot\text{hr}/\text{mL}$)	Unbound AUC_{24}^d ($\mu\text{g}\cdot\text{hr}/\text{mL}$)	C_{max}	AUC_{24}	
600	110	0.6	0.0972	2100	12	1.94	15.4	11.6	7.4
1200	350	1.1	0.150	7100	25	3.10	10.0	7.26	22
2000	700	1.9	0.308	15000	41	6.64	4.87	3.39	45

- a. Depending on the available safety and PK data, dose escalation may be adjusted to doses other than those outlined above with intermediate doses evaluated instead of or in addition to the planned dose levels with increments being $\leq\frac{1}{2}\text{-log}$ (ie, 3.3-fold) while following dose escalation and stopping rules outlined in [Section 6.6.1](#).
- b. Human exposure was predicted based on a minimal PBPK model using in vitro data and SimCYP predictions.
- c. Derived using exposure of PF-07059013 at NOAEL (1000 mg/kg/day) from 1 month dog toxicity study of unbound $C_{max} = 1.5 \mu\text{g}/\text{mL}$ and $AUC_{24} = 22.5 \mu\text{g}\cdot\text{hr}/\text{mL}$.
- d. Unbound values calculated taking into account plasma protein binding in humans($f_{up}=0.162$).

4.3.3.3. Rationale for Dose Selection in Part 3

Depending on emerging data from Part 1 (and if available, data from Part 2), if Part 3 is conducted, a single dose level of PF-07059013 will be studied, and the dose selected will be lower than the highest dose found to be safe and well tolerated in Part 1. Furthermore, the dose selected will be in the range of likely pharmacologically active doses.

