Part 3 of this study is designed to allow exploration of potential effects of food, particle size and tablet versus suspension formulation, on the PK of a single oral dose of PF-07059013. This part will be an open-label, randomized, 4-period crossover design. Approximately 8 healthy adult participants will be randomized in Cohort 8.

Depending on emerging data from Part 1 (dosing of suspension-small particle size under fasted condition), assessment of the effects of 1) high-fat/high-caloric meal versus a fasted state, 2) moderate particle size versus small particle size, and 3) tablet formulation versus

suspension-small particle size, on the pharmacokinetics of PF-07059013 may be undertaken in Part 3. The reference treatment and dose for Part 3 will be based on Part 1 (refer to [Section 4.3.3.3](#)). Part 3 will occur only after completion of Part 1, though it may occur in parallel to Part 2. The number of participants in Part 3 may be altered to randomize up to 12 healthy adult participants, depending on emerging PK data from Part 1 of this study.

For Part 1 and 3, between each dose administration to a given participant there will be a washout interval of at least 14 days. Participants may stay at the clinical research unit (CRU) for the duration of the washout period at the discretion of the investigator, this may be for safety or for logistic reasons. The washout interval may be adjusted based on data emerging from previous cohorts/periods. An on-site visit is scheduled for Day 8 (± 1 day) of Part 1 Period 3 and 4 only, and a telephone follow-up contact will occur 28 to 35 days after the last dose of investigational product in the final period. At the discretion of the investigator, telephone follow-up contact may be substituted with an on-site visit in case of additional follow-up of open AEs or clinically significant laboratory findings.

The total planned duration of participation, from the Screening visit to the Follow-up phone call, is approximately 15 weeks.

For Part 2, participants will be required to stay at the CRU for the duration of the treatment phase. An on-site follow-up visit will take place at Day 21 (± 1 day) and a telephone follow-up contact between Day 42 to 49. At the discretion of the investigator, telephone follow-up contact may be substituted with an on-site visit in case of additional follow-up of open AEs or clinically significant laboratory findings.

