In addition, dosing in the initial part of the study (Part 1) will be conducted in the fasting state (at least 10 hours) to facilitate management of any AEs which may occur shortly after dosing. For a given participant, dosing will be separated by ≥ 14 days. This planned dosing interval is deemed sufficient to permit washout of previous treatment based on the projected PF-07059013 effective half-life (see [Section 4.3.1](#)). Given that shorter effective half-life are anticipated at lower doses in Period 1 to 2 and to minimize burden on participants, additional visit on Day 8 is only planned for Period 3 and 4.

Part 2

Part 2 of this study is designed to assess the safety, tolerability, and PK, as well as potential PD of escalating doses of PF-07059013 administered for 14 days as a once-daily (QD) regimen. In addition, based on in vitro data (Section 2.2.2), potential of PF-07059013 to cause P450 CYP3A4 induction will also be explored. The proposed duration of dosing (14 days) is of shorter duration than the 30 days of non-clinical toxicology data currently available. This duration is also deemed to be sufficient to assess steady-state safety, PK, and PD given the projected effective half-life of PF-07059013 (see [Section 4.3.1](#)). The planned

doses in the escalation sequence (refer to [Section 6.6.1](#)) may be modified or repeated, as guided by emerging safety and PK data (as well as PD data, when available) but will follow the dose escalation rules defined in [Section 6.6.1](#).

To permit an unbiased assessment of safety, the administration of active versus placebo in each period will be double blinded to site staff (except those involved in preparation of doses) as well as the study participants. To permit real-time review of the safety, PK data (as well as PD data), a limited number of sponsor study team members will be unblinded (see [Section 9.5](#)).**Part 3**

Based on the biopharmaceutical profile of PF-07059013 (see [Section 2.2.4](#)) and preliminary in silico predictions, there is uncertainty in the potential impact of food on the rate and extent of absorption, hence preliminary evaluation of the effect of food on the PK of PF-07059013 is planned, to help guide the dose and dosing condition (fed versus fasting state) for future clinical studies with PF-07059013.

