To better understand and guide formulation development for future clinical studies, preliminary assessment of a tablet formulation and examination of different particle size is also planned.

Since the dose in this Part (refer to [Section 4.3.3.3](#)) will be selected based on observed safety and tolerability of single doses in Part 1 and the dose selected will be lower than the highest dose tested in Part 1, standard safety monitoring will be used in this part of the study, without placebo control, and without on-site visit following discharge.

For all parts of the study

Considering the nonclinical safety studies with PF-07059013 in mice and dogs (see [Section 2.2.3](#)), the standard safety assessments used by the sponsor in trials administering investigational product for the first time to humans are deemed suitable (see [Appendix 2: Clinical Laboratory Tests](#)). In addition to the standard safety assessments, levels of lactate (Part 1 to 3), EPO and reticulocyte count (Part 2 only) will also be monitored to evaluate the potential risk of reduction in tissue oxygen delivery per unit volume of blood, for this class of mechanism. Due to the long half-life of RBC and lag for EPO stimulation, any potential effects on reticulocyte count and EPO will likely only manifest after a sustained period, hence assessments are planned for Part 2, from Day 7 onwards for EPO and reticulocyte count. Ferritin levels and respiratory rate will be also assessed based on non-adverse findings in the nonclinical studies with PF-07059013 (see [Section 2.2.3](#)), with ferritin assessment planned on/after Day 5 due to physiologic rationale that this is likely the earliest point at which modulation of ferritin could be detected.

To ensure that participants with undiagnosed hematological conditions and elevated baseline lactate are not enrolled, hemoglobin, reticulocyte count (Part 2 only), lactate, PT/INR and aPTT levels will also be assessed at screening.

To further permit assessment of modulation of oxygen affinity and possibly limit excessive pharmacological effect, measures of hemoglobin oxygen affinity (p20 and p50) will be

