5.3.1. Meals and Dietary Restrictions

- Participants must abstain from all food and drink (except water) at least 4 hours prior to any safety laboratory evaluations, except for 8 hour post dose samples.
- For Part 1 and Part 3, water is permitted until 1 hour prior to dosing and during breakfast when dosing under fed (**high-fat/high-caloric**) condition. Water may be consumed without restriction beginning 1 hour after dosing.
- For Part 2, there are no water restriction prior to or after dosing.
- Noncaffeinated drinks (except grapefruit or grapefruit related citrus fruit juices see below) maybe consumed with meals and the evening snack.

Part 1 and when dosing under fasted condition in Part 3:

On Day 1 of each period, with dosing under fasted condition (overnight fast of at least 10 hours):

- Breakfast will not be provided.
- Lunch will be provided approximately 4 hours after dosing.
- Dinner will be provided approximately 9 to 10 hours after dosing.
- An evening snack may be permitted.

Part 2:

On all dosing days,

- A standard breakfast will be provided approximately 30 minutes prior to administration of the investigational product and is expected to be completed approximately 10 minutes prior to dosing. Participants will be encouraged to consume the entire meal. If participants are unable to complete the meals, the portion consumed in 25% increments will be documented and potential impact on results assessed by the Sponsor study team on a case-by-case basis.
- Lunch will be provided approximately 4 hours after dosing.
- Dinner will be provided approximately 9 to 10 hours after dosing.
- An evening snack may be permitted.

When dosing under fed (high-fat/high-caloric) condition in Part 3:

- Following an overnight fast of at least 10 hours, participants will receive high-fat (approximately 50% of the total caloric content of the meal)/high-caloric (approximately 800 to 1000 calories) breakfast approximately 30 minutes prior to administration of the investigational product on Day 1.
- The breakfast will be consumed over approximately a 20-minute period and the investigational product administered within approximately 10 minutes of completion of the meal. Participants will be encouraged to consume the entire meal. If participants are unable to complete the meals, the portion consumed in 25% increments will be documented and potential impact on results assessed by the sponsor study team on a case-by-case basis.

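### The roughly 2-fold exposure cover for the Part 2 starting dose rests on fasted Part 1 data, but Part 2 is dosed after breakfast and no food assumption is stated

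*Protocol*

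**What the plan says.** Section 4.3.3.2 of the protocol gives two protections for the first repeat-dose cohort.

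- Exposure: projected steady-state unbound Cmax and AUC "will be covered (approximately 2-fold lower) by exposures observed to have an acceptable safety profile in Part 1 of this study".
- Hb coverage: "Projected Hb coverage will not exceed that from Part 1, and will not be higher than 15" percent.

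The same section adds: "The proposed starting dose in Part 2 is 600 mg QD".

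The dosing conditions of the two parts differ. Section 4.2 says "dosing in the initial part of the study (Part 1) will be conducted in the fasting state", and Section 6.1.1 confirms this for all of Part 1. For all Part 2 dosing days, Section 5.3.1 says: "A standard breakfast will be provided approximately 30 minutes prior to administration of the investigational product".

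Section 2.2.4 calls the expected effect of food on exposure ambiguous, and Section 4.2 says "there is uncertainty in the potential impact of food on the rate and extent of absorption". Food is studied only in Part 3, with a high-fat, high-calorie meal. Section 4.3.3.3 makes Part 3 conditional, and Section 4.1 says "Part 3 will occur only after completion of Part 1, though it may occur in parallel to Part 2". Section 4.2 gives its purpose as guiding later studies. Part 2 opens after review of Part 1 Period 4 safety and PK data (Sections 4.1 and 4.3.3.2), which are also fasted.

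For Part 3, Section 4.2 justifies standard safety monitoring, with no placebo and no visit after discharge, by observed single-dose safety in Part 1 and because "the dose selected will be lower than the highest dose tested in Part 1".

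**The concern.** The cover compares exposures to be observed in Part 1, all fasted, with a projection for Part 2, which will be dosed fed. The comparison is sound only if the Part 2 projection already contains a food term, or if breakfast does not raise absorption materially. The documents state neither. Updating the model with Part 1 PK cannot settle it, because fasted data carry no information on food.

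The first fed dose in humans may therefore be the first day of a 14-day course, begun with less cover than Section 4.3.3.2 states. Section 4.3.3.1 reports a sensitivity analysis for 30% lower unbound intrinsic clearance at the Part 1 starting dose. No such analysis is reported for food. The Part 3 rationale has a similar gap: a dose below the Part 1 maximum does not by itself mean a fed exposure below the Part 1 maximum.

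**Working it through.** **Inputs** (unbound Cmax in µg/mL, unbound AUC24 in µg·h/mL)

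- Table 2, 600 mg QD: Cmax 0.0972, AUC24 1.94, coverage 7.4%.
- Table 2, 1200 mg QD: plasma Cmax 1.1, plasma AUC24 25, coverage 22%.
- Table 1, single doses: 3000 mg, 0.194 and 4.21, coverage 23%; 2000 mg, 0.147 and 3.08; 1000 mg, 0.0956 and 1.94.
- Fraction unbound in plasma 0.162; PK stopping limits 1.5 and 22.5.

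**Step 1. Reproduce the 2-fold figure.** Cover = Part 1 projection / Part 2 projection at 600 mg QD.

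- Against 3000 mg: 0.194/0.0972 = 2.00 (Cmax); 4.21/1.94 = 2.17 (AUC24).
- Against 2000 mg: 0.147/0.0972 = 1.51; 3.08/1.94 = 1.59.
- Against 1000 mg: 0.0956/0.0972 = 0.98; 1.94/1.94 = 1.00.

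The figure reproduces, but only against the top planned Part 1 dose.

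**Step 2. Food as a proportional change in absorbed dose.** The documents give no fed/fasted ratio F, so F is an assumption shown over a range. Under it, 600 mg behaves like 600 × F mg.

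Ratio at which coverage reaches 15%:

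- Linear: 600 + 600 × (15 − 7.4)/(22 − 7.4) = 912 mg, so F = 1.52.
- Log-log: slope = ln(22/7.4)/ln 2 = 1.572; F = (15/7.4)^(1/1.572) = 1.57.

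At F = 2 the 1200 mg row applies. Coverage is 22%, against 23% at the top of Part 1. For unbound exposure, the row's printed values (0.150 and 3.10) do not follow the table's own footnote. Plasma × 0.162 gives 1.1 × 0.162 = 0.178 and 25 × 0.162 = 4.05. Remaining cover is 0.194/0.178 = 1.09 and 4.21/4.05 = 1.04, so nearly all is used. On the printed values it would be 0.194/0.150 = 1.29 and 4.21/3.10 = 1.36. The coverage calculation does not use these unbound values.

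**Step 3. Unbound exposure itself proportional to F.** Cover = 0.194/(0.0972 × F) and 4.21/(1.94 × F). Coverage in the table is the log-log result from Step 2.

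| F | Coverage | Cmax cover | AUC24 cover |
|---|---|---|---|
| 0.8 | 5.2% | 2.49 | 2.71 |
| 1.0 | 7.4% | 2.00 | 2.17 |
| 1.25 | 10.5% | 1.60 | 1.74 |
| 1.5 | 14.0% | 1.33 | 1.45 |
| 2.0 | 22% | 1.00 | 1.09 |

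On this assumption the cover is gone at F of about 2.0 (Cmax) to 2.2 (AUC24). At F = 2 the margin to the PK stopping limits is 1.5/(0.0972 × 2) = 7.7 and 22.5/(1.94 × 2) = 5.8.

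**The case against.** The strongest reply is that a tolerated unbound exposure is a valid benchmark whatever meal state produced it, so the gap is only a missing statement about the Part 2 projection. That is right about the benchmark, and no two passages flatly contradict each other. But the projection is half of the comparison, and fasted data cannot validate it for fed dosing.

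The second reply is that other protections remain, and these stand:

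- Section 4.3.3.2 gives more than 11-fold multiples to the stopping limits at 600 mg QD.
- Section 4.3.3 cites about 40% coverage already studied in healthy adults without safety concerns, and Table 2 itself plans to 45%. The 15% figure is a limit on the starting dose, not a toxicity threshold.
- Participants are confined during treatment, fed PK is sampled from Day 1, and unblinded sponsor staff review data as they arrive.

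These limit the consequence, but they do not supply the stated 2-fold cover. The stopping limits come from the dog NOAEL and are a different protection. The escalation rules in Section 6.6.1 mainly protect the next cohort.

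The third reply is that absorption is expected to be moderate to good (Section 2.2.4) and was likely extensive in animals (Section 2.2.2), which leaves limited room for a rise. This makes a large ratio less likely but does not exclude one. Polymer was added in Part 1 to explore better absorption, which implies some room was thought possible.

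A reader might also infer that the design cannot yield a food result before Part 2. The text does not support that: Part 3 may run before, alongside or after Part 2, and is simply not required first. Even an early Part 3 would test a different meal. Nor does the meal change prevent assessment of repeat dosing, since Part 2 has its own fed profiles on Days 1, 7 and 14.

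**Conclusion.** The concern holds in a limited form. The protocol's arithmetic is right, but the cover in Section 4.3.3.2 is not established for fed dosing, because it depends on an unstated food assumption that Part 1 cannot test.

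Two stronger readings are tempting and unsupported. One is that the cover is exceeded or the starting dose unsafe. The documents give no food ratio, food may lower exposure, and at a ratio of 1.0 or below the cover stands. The other is that Part 1 is meant to cover the 15% limit. That limit is a separate, absolute bound on projected coverage, though it relies on the same projection.

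The sizes depend on the assumed mechanism: 15% coverage at a ratio of about 1.5 to 1.6 if absorbed dose scales, and loss of the unbound cover at about 2.0 to 2.2 if unbound exposure scales directly. They also assume that Part 1 reaches 3000 mg. The missing assumption itself is certain from the text. The point should be dealt with before Part 2 opens.

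**What to change.** Reconcile Sections 2.2.4, 4.2, 4.3.3.2, 5.3.1 and 6.1.1 before Part 2 opens.

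1. State in Section 4.3.3.2 whether Table 2 assumes fed or fasted dosing, and how fasted Part 1 data support fed Part 2 dosing.
2. Report the 2-fold cover and the Hb-coverage check over a stated range of fed/fasted ratios, in the manner of the clearance sensitivity in Section 4.3.3.1. The sponsor should choose and justify the range, since the documents supply none.
3. In Sections 4.2 and 4.3.3.3, express the Part 3 rationale in exposure terms for the fed treatment, as well as in dose.
4. Correct or explain the 1200 mg row of Table 2, whose unbound values do not follow its footnote.

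The cost is a few model runs and some added text. The downside is a less favourable stated margin. No dose, meal condition or order of parts is proposed; those remain with the sponsor and the investigator.

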- Dosing will be paused for any SAE that occurs in a participant receiving active treatment until causality is fully assessed by the PI and sponsor. Dosing may resume if the SAE is determined to be not drug-related by the PI and sponsor. If the SAE is determined to be either drug-related or unknown, either dosing will cease or the SAE will be evaluated by the sponsor's protocol review committee (or similar review group), which is independent of the study team and investigators. If the protocol review committee determines that dosing may resume, a plan that mitigates risks to participants with the resumption of dosing will be implemented. Such a plan could include a revision of inclusion/exclusion criteria, repeating or reducing the dose, or adding appropriate safety monitoring.
- It is determined that the limit of safety and/or tolerability has been reached. This decision will be made following discussions between the study team and the investigator.
- Other findings that, at the discretion of the study team and investigator, indicate that dose escalation should be halted.
- If, at any dose level, the average exposure reaches or exceeds the PK stopping limits: unbound plasma $C_{\text{max}} = 1.5 \mu\text{g}/\text{mL}$ or unbound plasma $AUC_{24} = 22.5 \mu\text{g}\cdot\text{hr}/\text{mL}$.
- If, based on the observed data, the group mean of unbound plasma C_{max} or AUC of the next planned dose is projected to exceed the escalation limits, that dose will not be explored. Modified doses may be explored if they are not expected to exceed PK stopping criteria.

Progression to the next dose will occur if the last dose was well tolerated and after satisfactory review of the available safety and PK data.

For Part 1, each dose escalation will be based on review of lactate and p50 data up to at least 8 hour post dose and all other safety data up to a minimum of 72-hours post dose plus PK assessments up to 24-hours post dose, in at least 5 out of 6 actively treated participants and at least 1 placebo-treated participant dosed in the previous dose level.

For Part 2, each dose escalation will be based on review of EPO and lactate data up to at least Day 7, reticulocyte and p50 data up to at least Day 14, and all other safety data up to Day 15 plus PK assessments up to Day 8, in at least 5 out of 6 actively treated participants and at least 1 placebo-treated participant dosed in the previous dose level.

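### Protocol Table 2: the 1200 mg QD row contradicts the table's own footnotes; its plasma values give safety margins of 8.4 (Cmax) and 5.6 (AUC24), not the printed 10.0 and 7.26

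*Protocol*

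**What the plan says.** Section 4.3.3.2 sends the reader to Table 2 for the Part 2 predictions: "safety margins relative to PK stopping limits set based on NOAEL from dog are summarized in Table 2". Two footnotes define how the columns connect.

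- Footnote d: "Unbound values calculated taking into account plasma protein binding in humans", with an unbound fraction in plasma of 0.162.
- Footnote c, on the margins: "Derived using exposure of PF-07059013 at NOAEL (1000 mg/kg/day) from 1 month dog toxicity study of unbound" Cmax 1.5 µg/mL and AUC24 22.5 µg·hr/mL.

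Table 1 (single doses, Part 1) carries the same two footnotes.

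The row in question reads "1200 350 1.1 0.150 7100 25 3.10 10.0 7.26 22". In column order this is dose, blood Cmax, plasma Cmax, unbound Cmax, blood AUC24, plasma AUC24, unbound AUC24, Cmax margin, AUC24 margin and maximum Hb coverage (%).

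**The concern.** Anyone who multiplies the row's plasma values by the stated fraction gets higher unbound exposures than those printed, and therefore smaller margins. Neither footnote gives another fraction or method for this row.

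This is a first-in-human study in healthy volunteers who can expect no benefit, and Table 2 is where the protocol states the predicted margins for the repeated-dose cohorts. Section 4.3.3.2 also ties the size of escalation increments to predicted unbound exposure, which is the column affected. If the plasma values are right, the middle planned dose looks further from the dog NOAEL exposure than the model predicts. If the unbound values are right, the plasma, blood and Hb coverage cells are wrong instead. In both cases the row misinforms the reader.

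**Working it through.** **Inputs.** Unbound fraction 0.162 (footnote d); reference exposures 1.5 µg/mL and 22.5 µg·hr/mL (footnote c); plasma, unbound and margin cells from Protocol Tables 1 and 2.

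**Formulas.** Unbound = plasma × 0.162. Cmax margin = 1.5 / unbound Cmax. AUC24 margin = 22.5 / unbound AUC24.

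**All nine rows.** Each cell shows the printed value, then the value recomputed from plasma.

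| Row | Unbound Cmax | Unbound AUC24 | Cmax margin | AUC24 margin |
|---|---|---|---|---|
| Table 1, 100 mg | 0.0227 / 0.0227 | 0.324 / 0.324 | 66.1 / 66.1 | 69.4 / 69.4 |
| Table 1, 250 mg | 0.0421 / 0.0421 | 0.713 / 0.713 | 35.6 / 35.6 | 31.6 / 31.6 |
| Table 1, 500 mg | 0.0632 / 0.0632 | 1.22 / 1.215 | 23.7 / 23.7 | 18.5 / 18.5 |
| Table 1, 1000 mg | 0.0956 / 0.0956 | 1.94 / 1.944 | 15.7 / 15.7 | 11.6 / 11.6 |
| Table 1, 2000 mg | 0.147 / 0.147 | 3.08 / 3.078 | 10.2 / 10.2 | 7.31 / 7.31 |
| Table 1, 3000 mg | 0.194 / 0.194 | 4.21 / 4.212 | 7.72 / 7.72 | 5.34 / 5.34 |
| Table 2, 600 mg QD | 0.0972 / 0.0972 | 1.94 / 1.944 | 15.4 / 15.4 | 11.6 / 11.6 |
| **Table 2, 1200 mg QD** | **0.150 / 0.178** | **3.10 / 4.05** | **10.0 / 8.42** | **7.26 / 5.56** |
| Table 2, 2000 mg QD | 0.308 / 0.308 | 6.64 / 6.642 | 4.87 / 4.87 | 3.39 / 3.39 |

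In the eight rows that reproduce, printed unbound divided by printed plasma is 0.1615 to 0.1627. At 1200 mg QD it is 0.150/1.1 = 0.136 for Cmax and 3.10/25 = 0.124 for AUC24, so no single alternative fraction explains the row.

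**Where the break lies.** The printed margins follow from the printed unbound values: 1.5/0.150 = 10.0 and 22.5/3.10 = 7.26. The fault is between the plasma and unbound columns and carries through to the margins. Four mutually consistent cells also make a misread digit unlikely.

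**Rounding.** A plasma Cmax printed as 1.1 lies in 1.05–1.15, so the margin lies between 1.5/(1.15 × 0.162) = 8.05 and 1.5/(1.05 × 0.162) = 8.82. A plasma AUC24 printed as 25 lies in 24.5–25.5, so the margin lies between 22.5/(25.5 × 0.162) = 5.45 and 22.5/(24.5 × 0.162) = 5.67. The printed 10.0 and 7.26 are outside both ranges.

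**Which cells are likelier to be wrong.**

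- The row's blood Cmax 350, blood AUC24 7100, plasma 1.1 and 25, and Hb coverage 22% sit next to the 3000 mg single-dose row, "3000 370 1.2 0.194 7300 26 4.21 7.72 5.34 23".
- Its unbound values and margins instead sit next to the 2000 mg single-dose row, "2000 230 0.91 0.147 4600 19 3.08 10.2 7.31 15", where coverage is 15%.
- The printed unbound values imply plasma of 0.150/0.162 = 0.926 and 3.10/0.162 = 19.1. Linear interpolation between those two Table 1 rows gives about 15.4% coverage and blood Cmax about 238 at plasma Cmax 0.926, and blood AUC24 about 4650 at plasma AUC24 19.1. The row prints 22%, 350 and 7100.

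**Relative to the highest planned Part 1 dose (3000 mg).** As printed: 0.150/0.194 = 77% and 3.10/4.21 = 74% of its unbound exposure. Recomputed: 0.178/0.194 = 92% and 4.05/4.21 = 96%.

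**Escalation steps in predicted unbound exposure.**

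| Step | Cmax, printed | Cmax, recomputed | AUC24, printed | AUC24, recomputed |
|---|---|---|---|---|
| 600 to 1200 mg | 1.54× | 1.83× | 1.60× | 2.08× |
| 1200 to 2000 mg | 2.05× | 1.73× | 2.14× | 1.64× |

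With rounding of the plasma values, the recomputed 600 to 1200 mg step is 1.62–2.09× (Cmax) and 1.96–2.22× (AUC24). All steps are below the 3.3-fold cap.

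**The case against.** The inconsistency is hard to dispute; the case on the other side is about how much it matters and which cells are wrong.

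- **No decision depends on the cells.** Under Section 6.6.1 a dose is ruled out on a projection from human data ("If, based on the observed data, the group mean of unbound plasma" Cmax or AUC), and escalation needs satisfactory review of the preceding dose level. By the time 1200 mg QD is considered, Part 1 and 600 mg QD data will have replaced this prediction. The text of Section 4.3.3.2 does not cite the 1200 mg margins. This stands and limits the consequence.
- **Margins of this size are already disclosed.** Section 2.2.3 gives dog margins of 8.6 and 5.8 at the projected efficacious exposure, and Table 2 itself shows 4.87 and 3.39 at 2000 mg QD. This also stands: the recomputed margins reveal no new level of risk.
- **The error is not unfavourable in every respect.** Correcting the unbound cells enlarges the 600 to 1200 mg step but shrinks the step to 2000 mg, the highest planned exposure. The recomputed steps also fit better with the stated aim of smaller increments above the efficacious dose. This is fair: the error is in the unsafe direction for the margins at 1200 mg, not for the whole ladder.
- **The printed values might come from a different model run.** Section 4.3.2 projects 0.18 and 3.9 at 1500 mg QD in sickle cell patients; scaling by 1200/1500 gives 0.144 and 3.12, close to 0.150 and 3.10. But Table 2 concerns healthy participants, and its other rows do not scale this way: the same rule gives 0.072 and 1.56 at 600 mg (printed 0.0972 and 1.94) and 0.24 and 5.2 at 2000 mg (printed 0.308 and 6.64). It is a possible source of the error and does not reconcile the row.

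**Conclusion.** The concern holds. The 1200 mg QD row of Table 2 is inconsistent with footnotes c and d, and that conclusion needs nothing beyond the printed numbers and the stated rules.

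Taking the plasma values as correct, unbound exposure is understated by 16% (Cmax) and 23% (AUC24). The margins are overstated by 19% (13–24% allowing for rounding) and 31% (28–33%). That the plasma values are the correct ones is an inference from the rest of the row, since the model output is not in the documents.

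The practical effect is small. The recomputed margins fall within the range shown for other planned doses, and predicted unbound exposure stays below that of the 3000 mg single dose on either reading. No stopping limit, increment cap or escalation rule is breached. It should still be corrected, because it is a stated safety margin for a planned first-in-human dose.

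**What to change.** Check the model output for 1200 mg QD in healthy participants.

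- If plasma Cmax 1.1 and AUC24 25 are confirmed, change four cells: unbound Cmax to 0.178, unbound AUC24 to 4.05, and the margins to 8.42 and 5.56.
- If the unbound values 0.150 and 3.10 are confirmed, correct the row's plasma, blood and Hb coverage cells from the model output.

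The cost is one source check and a few table cells in the next amendment. Design, doses and rules stay as they are. On the likelier reading, the stated margins for this dose become less favourable.
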